4.5.9 Seizure Data

The seizure frequency (per 28 days) and percentage change from baseline for total seizures, drop seizures and convulsive seizures during the study will be evaluated for each of the following 12 week periods:

- Week 1 (Day 1) to Week 12 (Day 84)
- Week 13 (Day 85) to Week 24 (Day 168)
- Week 25 (Day 169) to Week 36 (Day 252)
- Week 37 (Day 253) to Week 48 (Day 336)
- Week 49 (Day 337) to Week 60 (Day 420)
- Week 61 (Day 421) to Week 72 (Day 504)
- Week 73 (Day 505) to Week 84 (Day 588)
- Week 85 (Day 589) to Week 96 (Day 672)
- And so on for each 12-week interval

Please note that drop seizures are recorded for LGS patients only.

The percentage change from the baseline period each of the above periods will be presented, including for the last 12 weeks (Section 4.1.4.3).

Percentage change from the baseline period will be calculated as:

$$\left(\frac{\text{Frequency during the individual period} - \text{frequency during baseline period in core study}}{\text{frequency during baseline period in core study}} \right) \times 100$$

In this study, seizures are recorded on a weekly basis whereas in all core studies, seizures are recorded on a daily basis. Caregivers/patients are expected to call the IVRS system to record the frequencies of seizure subtypes experienced every 7 days from Visit 1 (Day 1) until the end of their participation. The frequency during each of the periods mentioned above will be based on 28-day averages and will be calculated as:

$$\text{Average number of seizures per day in the period} \times 28$$

All calls that take place during the period in question will contribute to the calculation of the average number of seizures per day in that period.

The average number of seizures per day in the period will be calculated as the average of:

$$\frac{\text{Number of seizures reported}}{\text{Number of days since last call}}$$

The number of days since the last call will be calculated as follows, and is dependent on whether the call took place <7, 7 or >7 days after the previous call (or after the date of Visit 1 (Day 1) in the case of the first call in the first period):

- If the call takes place exactly 7 days after the previous call, then the number of days since the last call will be 7.
- If the call takes place <7 days after the previous call, then the number of days since the last call will be calculated as:

$$(\text{Date of current call} - \text{date of previous call}) + 1$$

- If the call takes place >7 days after the previous call, then the number of days since the last call will be 7.

For the seizure types and periods listed above, summary statistics will be presented for raw seizure frequencies and percentage change from baseline from core study baseline period. In addition, the number of patients with $\geq 25\%$, $\geq 50\%$, $\geq 75\%$ and 100% reduction in seizure frequency will be presented.

Furthermore, the percentage change from the core study baseline period will be presented for convulsive seizures from Dravet patients only and for drop seizures for LGS patients only.

All outputs will be repeated with the inclusion of an LOCF imputation step, which is described in the following steps:

- If a patient has valid data for ≥ 1 consecutive periods from and inclusive of the first period but only missing periods thereafter, then imputation of the missing period(s) will be carried out using the last 12 weeks of valid data (see Section 4.1.4.3).
- If a patient has intermittent missing periods (i.e. ≥ 1 missing period that falls after a populated period 1 and before subsequent populated periods), then the missing period(s) will be imputed with the closest earlier non-missing period of data.
- If the patient has ≥ 1 consecutive periods of missing data from and inclusive of the first period then no imputation will occur and data from the patient will be excluded from any LOCF presentations.

Summaries related to seizures as presented in this section and subsequent sections will include patients from all core studies except GWEP1332 Part A, from which data will be listed only.

The seizure frequency (per 28 days) and percentage change from baseline for total seizures, drop seizures and convulsive seizures during the study will be evaluated for the periods described in Section 4.5.9 and for the following subgroups:

- Patients taking clobazam
- Patients not taking clobazam
- Core study actual treatment: GWP42003-P
- Core study actual treatment: Placebo
- Patients taking clobazam; core study actual treatment: GWP42003-P
- Patients not taking clobazam; core study actual treatment: GWP42003-P
- Patients taking clobazam; core study actual treatment: Placebo
- Patients not taking clobazam; core study actual treatment: Placebo
- Patients with data at Week 37 (Day 253) to Week 48 (Day 336) [^]
- Patients with data at Week 37 (Day 253) to Week 48 (Day 336); patients taking clobazam [^]
- Patients with data at Week 37 (Day 253) to Week 48 (Day 336); Patients not taking clobazam [^]

[^] Only for convulsive and drop seizures.

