9.1.12 Patient Diary

Seizure information (number and type of seizures) will continue to be collected through an IVRS telephone diary, completed weekly until the ‘End of Treatment’/Withdrawal visit. In addition, patients/caregivers will be instructed to complete the diary using IVRS at the following times:

- Once on the day before the ‘End of Taper Period’ visit.
- Once on the day before the Follow-up visit.

The patient or their caregiver will also continue to complete a paper diary daily to record daily usage of IMP, rescue medication, concomitant AEDs and AEs. Adequate training will be provided to the patient/caregiver in order to ensure data is being accurately collated via IVRS and paper diaries.

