9.2.12 End of Treatment/Withdrawal Visit

This visit will take place after a maximum of 4 years' (208 weeks after Visit 1) treatment (as detailed below), or following early withdrawal from the study.

- A patient with at least 2 years' participation in the OLE (≥ 104 weeks after Visit 1) will complete the OLE phase when GWP42003-P is approved in their indication and is commercially available. Patients will complete an unscheduled 'End of Treatment' visit to transition from OLE to commercial product. The timing will vary per patient and is projected to begin in February 2019.
- A patient with less than 2 years' participation in the OLE when GWP42003-P is approved in their indication and is commercially available will continue the OLE phase until reaching a maximum of 2 years' OLE treatment, at which point an unscheduled 'End of Treatment' visit will be conducted. The unscheduled 'End of Treatment' visit will be conducted no earlier than 730 days after Visit 1.
- Patients who do not continue treatment with GWP42003-P will be scheduled for an 'End of Taper' visit.

The following assessments will be made at the 'End of Treatment'/Withdrawal visit: vital signs, physical examination (including height and body weight), effects on menstruation cycles (for females), Tanner Staging (for patients aged 10–17 [inclusive], or earlier if clinically indicated by onset of menarche or other signs of precocious puberty), ECG, C-SSRS, Vineland-II, cognitive assessment battery (participating centers only), QOLCE/QOLIE, S/CGIC and S/CGICSD. Clinical laboratory samples (blood and urine [where possible]) will be taken for determination of serum IGF-1 levels (for patients less than 18 years of age), hematology,

biochemistry, a pregnancy test (if appropriate, using a serum sample) and urinalysis. The patient's IVRS report and paper diary will be reviewed and the information recorded along with information regarding AEs, IMP, epilepsy-related hospitalizations, concomitant medications and/or changes to medication. The Investigator must assess adherence to the dosing regimen.

The cognitive assessment battery items will only be administered at a sub-group of centers that have the expertise to conduct the assessments (ideally before any other study procedures but can be completed on a separate day, if necessary, within 3 days of the visit) and will only be administered to patients who underwent cognitive testing during their Core Study.

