9.2.15 Follow-up Visit

This visit is required for patients who withdraw from the study or complete treatment but do not wish to continue to use GWP42003-P. The Follow-up visit will be performed 4 weeks (+ 3 days) after the patient's last dose of GWP42003-P (including final taper period dose) and can be conducted over the telephone. During this visit/call, caregivers will be asked for information on AEs, epilepsy-related hospitalizations, concomitant medications and/or changes to medication. The CWS/PCWS will also be administered.

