4. STATISTICAL METHODS

4.1 General Considerations

All tables will be presented by indication (where appropriate), including an overall count, as follows:

Dravet Syndrome (N=XX)	Lennox-Gastaut Syndrome (N=XX)	Overall (N=XX)
------------------------	--------------------------------	----------------

In all tables, listings and figures, the study visits will be referred to and labelled as per [Table 2](#)

Table 2 Study Visits

Actual Visit	Visit Label
Visit 1: Day 1	Day 1
Visit 2: Day 15	Day 15
Visit 3: Day 29	Day 29
Visit 4: Day 85	Day 85
Visit 5: Month 6 or Week 24	Week 24
Visit 6: Month 9 or Week 38	Week 38
Visit 7: Week 48 or End of Treatment (only patients who completed at 1 year)*	Week 48
Visit 8: Week 76	Week 76
End of Treatment (only patients who completed on or after Day 400)*	End of Treatment

End of Treatment (withdrawn patients only)	End of Treatment
End of Taper	End of Taper
Post-Taper Safety Call	Post-Taper Safety Call
Safety Follow-Up	Safety Follow-Up

* For some patients, the end of treatment visit occurs after one year in the OLE, whereas for other patients the end of treatment visit occurs after two or more years in the OLE.

Unless stated otherwise, continuous variables will be summarized showing the number of non-missing values (n), mean, standard deviation, median, minimum and maximum and categorical variables will be summarized showing the number and percentage of patients falling in each category. For continuous summaries of seizure frequency, the lower and upper quartiles will also be presented.

Minimum and maximum values will be presented to the same decimal precision as the raw data. Mean and median will be presented to one more decimal place than the raw data, and standard deviation to 2 more decimal places than the raw data. Percentages will be presented to one decimal place.

For patients who enter the OLE on the same day as the core study end of treatment or end of taper visit, the CRF for this study did not require some data to be entered for a second time. Hence, for visit based endpoints, if a patient does not have data entered in this study at Visit 1, then data from the end of treatment or end of taper visit in the core study will be used, provided that the date of collection is on Day 1 of the OLE.

Unless otherwise stated, all summaries will be presented by indication.

All analyses and summaries will be produced using SAS Version 9.4.

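### SAP 4.5.9 sets no minimum coverage and no end-of-treatment cut for completers' 12-week seizure periods, so a final period can show a 100% reduction on one call, possibly off treatment

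*SAP*

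**What the plan says.** SAP 4.5.9 divides follow-up into 84-day periods counted from Day 1. It says that "All calls that take place during the period in question will contribute to the calculation of the average number of seizures per day". Its formula follows: "The average number of seizures per day in the period will be calculated as the average of" the seizures reported at each call divided by the days since the last call. The result is multiplied by 28. The divisor is 7 when the gap between calls is 7 days or more, and the gap plus 1 when it is shorter. For each period the SAP counts patients with reductions of at least 25%, 50% and 75%, and "100% reduction in seizure frequency will be presented".

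No section sets a minimum number of calls or days. The LOCF rules speak of valid, populated and missing periods but define none of these terms.

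Two limits exist elsewhere in the SAP. Section 4.1.2.1 confines a withdrawn patient's data to the time before withdrawal. Section 4.1.4.3 ends the last-12-weeks window no later than the last dose recorded on the end-of-treatment form. Section 4.5.9 applies no such cut to completers' 12-week periods.

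Protocol 9.1.12 asks for weekly IVRS calls up to the End of Treatment/Withdrawal visit, then one the day before the End of Taper visit and another: "Once on the day before the Follow-up visit". Protocol 9.2.13 places End of Taper 10 (+3) days after end of treatment. On the later visit, Protocol 9.2.15 says: "The Follow-up visit will be performed 4 weeks (+ 3 days) after the" patient's last dose, taper included. Under Protocol 9.2.12 the unscheduled end-of-treatment "visit will be conducted no earlier than 730 days after Visit 1".

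**The concern.** SAP 2.2 lists the numbers of patients free of convulsive seizures (DS) and of drop seizures (LGS) as objectives. The only planned output that answers them is the 100% row of the responder tables (9.7.1–9.7.6). A reader will take that row as freedom from seizures over 12 weeks on treatment. As written, it can rest on one weekly report, and in some patients that report dates from after dosing stopped.

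If each call covers at most 7 days, seeing fewer days can only make an all-zero period more likely, so short coverage pushes the 100% count upwards among populated periods. In the other three rows it adds noise in either direction. Off-treatment calls have no fixed direction. Late periods hold fewer patients, so a few such values weigh more there.

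**Working it through.** The documents give no figure to reproduce. The inputs are the SAP 4.5.9 rule and period boundaries, weekly calls from Day 1, and the Protocol visit timings above. End dates and seizure rates are assumptions where marked.

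1. **One zero call.** Frequency = 28 × 0/7 = 0. Change = (0 − B)/B × 100 = −100% for any baseline B above 0. The patient enters all four rows on at most 7 of 84 days.

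2. **Calls per period.** Period p runs from Day 84(p−1)+1 to Day 84p, and calls fall on Day 1+7j. Period 1 holds 11 calls (Days 8 to 78) and each later complete period holds 12. Under weekly calling, only the period in which participation ends, or one reached by a post-treatment call, is short.

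3. **Ending w days into a period after the first.** Calls in that period = floor((w−1)/7)+1.
   - Withdrawal: one call for w = 1 to 7. With evenly spread dates (assumption) that is 7/84 = 8.3%. If a call on the withdrawal date itself is left out, w = 2 to 8 gives the same share.
   - Completion on Days 337–343: one call, Day 337. The previous call was on Day 330, so at most one reported day lies within Days 337–420.
   - Completion on Day 366: calls on Days 337, 344, 351, 358 and 365, so five.
   - Completion on Days 757–763, which the current Protocol allows: one call, Day 757.

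4. **Completer who tapers, end of treatment on Day E.** The call before End of Taper falls on E+9 to E+12. The last taper dose is on about E+9 to E+10. Follow-up comes 28 to 31 days after that dose, so the call the day before falls on (E+9)+28−1 = E+36 to (E+10)+31−1 = E+40. For E = 731:
   - Days 740–743 lie in Days 673–756;
   - Days 767–771 lie in Days 757–840, where this is the only call, about four weeks off drug.

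   Taking the two calls at E+9 and E+37, the second is alone in the next period when w+9 ≤ 84 and w+37 > 84, that is w = 48 to 75. That is 28/84 = 33% of end dates for tapering completers, if evenly spread (assumption).

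5. **Chance of an all-zero period**, exp(−rate × days/28), for assumed Poisson rates:

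| Rate per 28 days | 7 days | 35 days | 84 days |
|---|---|---|---|
| 1 | 0.78 | 0.29 | 0.05 |
| 4 | 0.37 | 0.007 | 0.000006 |
| 12 | 0.05 | 0.0000003 | about 0 |

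6. **Equal weighting.** Gaps of 7 days or more all take divisor 7, so the plain mean equals total seizures over total SAP days unless a call comes less than 7 days after the previous one. (A 6-day gap also gets 6+1 = 7, so only gaps of 5 days or less matter.) Take eleven weekly calls of 3 seizures plus a zero call one day later:
   - SAP rule: (11 × 3/7 + 0/2)/12 × 28 = 11.0.
   - Pooled on the SAP's own divisors: 33/(77+2) × 28 = 11.7.
   - At a baseline of 22 these are −50.0% and −46.8%, on either side of the 50% threshold.

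7. **LOCF.** Trailing gaps are filled from the last 12 weeks, so a lone call is usually not carried forward. But a period with one call is not missing, so its value stands in the LOCF tables for that period and can fill a later intermittent gap.

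**The case against.** The best reply is that this is a corner of a descriptive output. Under weekly calling only end-of-participation periods are sparse. Taper calls apply only to completers who do not continue the product, and Day 731 is the earliest date for that unscheduled visit, not a typical one. If 5% of patients withdraw in a period (assumption), one-call false 100% reductions come to 0.05 × 0.083 × 0.37 = 0.15% of patients at 4 seizures per 28 days, and 0.05 × 0.083 × 0.78 = 0.3% at 1. The last-12-weeks summary is reported alongside, and the diary data are listed. The coverage rule is also read from silence, since a valid period is never defined. All of this stands and limits the size of the point. It does not supply a coverage rule or exclude post-treatment calls, and completion dates clustered just after a boundary would raise the share.

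Two stronger readings are tempting and not supported. A reader might infer that the call schedule by itself gives every Week 48 completer a one-call period. The footnote to SAP Table 2 says "For some patients, the end of treatment visit occurs after one year in the OLE", and the table separates other completers at Day 400 or later. That fits completion near Day 366, with five calls, at least as well as Days 337–343. A reader might also infer that the divisor is wrong. It would be right if a call covers the previous call's day to the current day, up to 7 days. No section states the recall window, so no error is shown.

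**Conclusion.** The point holds for the end of participation. SAP 4.5.9 as written lets a final 12-week period count as a 100% reduction on a single call, and lets calls made after treatment enter completers' periods, although the last-12-weeks window in SAP 4.1.4.3 stops at the last dose. The 8% (withdrawals) and 33% (tapering completers) rest on evenly spread end dates and weekly calling. The zero-seizure probabilities rest on assumed Poisson rates. The documents give none of these, so the effect on the reported counts is unknown and may be small. Equal weighting is a minor flaw that acts only when a call is early. No hypothesis test is affected, and the primary safety endpoint is untouched. The change is worth making because the 100% row carries a stated objective and the correction is cheap.

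**What to change.** - **Rate.** Compute each period's frequency as 28 × total seizures / total days covered. Take the days covered from the IVRS recall window, confirm that window and state it in SAP 4.5.9.
- **End of treatment.** Limit the on-treatment 12-week periods to calls up to the last treatment-phase dose, for completers as well as withdrawals. List later calls separately.
- **Coverage.** Count a patient in a period's responder rows, all four with one common denominator, only when covered days reach a pre-specified minimum. Otherwise class the period as not evaluable. Keep the all-available-data version as a sensitivity table and report days covered per period.
- **LOCF.** Do not use the minimum to redefine valid data. SAP 4.5.9 excludes from LOCF any patient whose first period is missing, so a minimum there would drop early withdrawals. Flag LOCF values that rest on below-minimum coverage instead.

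The cost is SAP wording and one reprogrammed derivation. No new data are needed, since the diary is already listed (Listings 9.1.1 and 9.1.2). The downside is fewer evaluable final periods and possibly lower 100% counts. The minimum needs care: a weekly caller ending on Day 731 has 9 calls (Days 673 to 729), or 9 × 7 = 63 days, in Days 673–756, so a 63-day rule would sit exactly on that edge. With evenly spread dates, 56/84 (67%) of withdrawals after the first period would fall below it.

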All IMP (used and unused) will be collected and a check of the returned IMP against usage should be made. For patients who withdraw early or who do not transition to commercial product, the IVRS will be contacted to confirm withdrawal from the study. For patients who immediately continue to use GWP42003-P following the 'End of Treatment' visit, the IVRS will be contacted to confirm the patient's completion of this study and the paper diaries will be collected. For patients 12 years of age and older, the trained Investigator or study coordinator will complete the Study Medication Use and Behavior Survey as an interview with the patient/caregiver.

For patients who do not immediately continue to use GWP42003-P following the 'End of Treatment' visit, IMP will be down-titrated at home (10% per day for 10 days). Additional IMP will be dispensed, if required. Patients who withdraw early should also begin the taper period following the Withdrawal visit (unless continued dosing is not possible due to an AE). The IVRS will generate the patient's daily IMP dosing volumes for the 10-day taper period, during which time diary information will continue to be recorded in the paper diary.

Following the 'End of Treatment'/Withdrawal visit, the IVRS seizure reporting diary should only be completed on the day before the 'End of Taper Period' visit and on the day before the Follow-up visit.

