4.1.2 Handling of Missing Data

4.1.2.1 Seizure Data

If a patient withdraws during the time after which they have taken their first dose in the OLE, then seizure frequencies will be calculated from all the available data prior to the patient withdrawing.

Last observation carried forward (LOCF) methodologies that will be carried out on seizure data are discussed in Section 4.5.9.

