4.1.4.3 Last 12 Weeks

The last 12 weeks (84 days) for IVRS based endpoints is defined as all available data from 12 weeks prior to the earliest of the date of the patient completing/withdrawing from the study, the last call to IVRS, or the last dose date as recorded on the "End of Treatment Study Outcome" page of the CRF.

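### The 12-week seizure periods in SAP 4.5.9 have no end-of-treatment cut-off for completers, so taper and off-drug diary calls enter them for completers who stop GWP42003-P

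*SAP*

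**What the plan says.** SAP 4.5.9 divides follow-up into consecutive 84-day periods from Day 1, with no last period named ("And so on for each 12-week interval"). Calls are expected "every 7 days from Visit 1 (Day 1) until the end of their participation", which is not the same as the end of dosing. For each period, "All calls that take place during the period in question will contribute to the calculation of the average number of seizures per day". When a call is late, the divisor is fixed: "If the call takes place >7 days after the previous call, then the number of days since the last call will be 7".

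Under Protocol 9.2.12, after the End of Treatment or Withdrawal visit "the IVRS seizure reporting diary should only be completed on the day before" the End of Taper visit and again on the day before the Follow-up visit. Protocol 9.1.12 lists the same two calls. They apply to patients who withdraw and to completers who do not go on using the drug (Protocol 9.2.13 and 9.2.15).

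The SAP has two cut-offs. Section 4.1.2.1 says that, for a patient who withdraws, "seizure frequencies will be calculated from all the available data prior to the patient withdrawing". Section 4.1.4.3 ends the last-12-weeks window at the earliest of completion or withdrawal, "the last call to IVRS, or the last dose date as recorded" on the end-of-treatment page of the case report form. Neither is written for the 12-week periods of a completer.

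**The concern.** The 12-week periods feed the seizure-frequency and responder tables (SAP Tables 9.1.x and 9.7.x), which serve the objective on maintained seizure reduction. A reader will take each period as describing patients on GWP42003-P. For a completer who stops, a late period can instead hold a taper call and an off-drug call with few or no treated calls beside them.

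The SAP is also inconsistent with itself. The last-12-weeks summary stops at the last dose, and the definition of last visit (4.1.4.2) leaves out the end-of-taper and follow-up visits. The 12-week periods have no matching line, so two programmers could build different tables from the same data.

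**Working it through.** The plan states no figure to reproduce. The check places each call in its period.

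**Inputs**
- Day numbering (SAP 4.1.3): 730 days after Visit 1 is Day 731.
- Period number = floor((day − 1)/84) + 1 (SAP 4.5.9).
- Weekly calls on Days 8, 15, 22 and so on, up to and including EOT.
- End of Taper visit 10 (+3) days after EOT (Protocol 9.2.13), so the taper call is at EOT + 10 − 1 = EOT + 9.
- Follow-up visit 4 weeks (+3 days) after the final taper dose (Protocol 9.2.15), so the call is at EOT + 10 + 28 − 1 = EOT + 37.
- EOT times: Week 48, Day 337 (SAP Table 2, patients completing at one year); 730 days, Day 731 (Protocol 9.2.12); 208 weeks, Day 1457 (Protocol 4.1).

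**Calls per period**

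| EOT | Period | Calls up to EOT | Taper call | Follow-up call | After EOT |
|---|---|---|---|---|---|
| Day 337 | Weeks 49–60 (Days 337–420) | 1 | Day 346 | Day 374 | 2 of 3 |
| Day 731 | Weeks 97–108 (Days 673–756) | 9 | Day 740 | – | 1 of 10 |
| Day 731 | Weeks 109–120 (Days 757–840) | 0 | – | Day 768 | 1 of 1 |
| Day 1457 | Weeks 205–216 (Days 1429–1512) | 5 | Day 1466 | Day 1494 | 2 of 7 |

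The 3-day allowances on the two visits change none of these rows. Moving the Week 48 EOT by its 7-day window gives 2 of 2 (Day 330) or 2 of 4 (Day 344). If one year means Day 365, the share is 2 of 7.

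**All 84 positions of EOT within a period.** In 28 positions a period holds only the Follow-up call. In 9 more it holds only the taper and Follow-up calls, making 37 of 84 (44%) with post-EOT calls alone. In a further 7 (8%) post-EOT calls are the majority. These are calendar positions, not shares of patients.

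**Illustration.** Assume a 50% reduction on drug, a return to baseline off drug, and a taper-call rate t between 0.5 and 1 times baseline.
- Day 337, Weeks 49–60: (0.5 + t + 1)/3 = 0.67 to 0.83, a change of −33% to −17%.
- Day 731, Weeks 109–120: 1/1, a change of 0%.
- Day 1457, Weeks 205–216: (5 × 0.5 + t + 1)/7 = 0.57 to 0.64, a change of −43% to −36%.

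If the reduction persisted after stopping, all three would show −50% and nothing would be distorted.

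**Divisor.** The Follow-up call comes about 28 days after the taper call (374 − 346; 768 − 740) but is divided by 7. If it reports the past 7 days, there is no inflation. If it reports the whole gap, the rate is inflated 28/7 = 4-fold. The documents do not give the recall period.

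**LOCF.** SAP 4.5.9 imputes missing periods only. Weeks 109–120 of the Day 731 completer contain a call, so that period is not imputed. Later empty periods are filled from the last 12 weeks, which are cut at the last dose. The patient's LOCF series then has one off-drug value between on-drug values.

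**The case against.** Several points on the other side stand. Few patients may be affected: those who move straight to commercial product have no taper or Follow-up call, and the 2-year completion route is designed for that transition. Withdrawals are cut by SAP 4.1.2.1, if withdrawing means the Withdrawal visit. The taper call reflects a falling dose, so only the Follow-up call is strictly off drug. SAP 4.5.9 speaks of seizures during the study and never labels the periods as on-treatment. The last-12-weeks summary, and the trailing LOCF values drawn from it, are already protected. These are descriptive secondary summaries without hypothesis tests, and if seizures rise off drug the error works against the drug.

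It might also be argued that SAP 4.1.2.1 reaches these completers, because Protocol 9.2.12 has the site register patients who do not transition as withdrawn in the telephone system. But SAP Table 2 and SAP 4.4.2 separate completers from withdrawn or discontinued patients, so that reading is not secure.

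The number and spacing of calls are not settled either. Protocol 8.1.2 and Section 10 have telephone recording continue during taper, and Appendix 1 lists seizure details at the post-taper safety call; these sit badly with the restriction in Protocol 9.2.12. Extra calls would shorten the gap before the taper call, but they would also add post-EOT calls to the periods. They do not supply the missing cut-off.

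A reader might infer that the 12-week results as a whole are built mainly from off-drug data, or that follow-up rates are inflated 4-fold. The documents support neither. The first needs the number of completers who stop, which is not given; the second needs a recall period that is not stated.

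**Conclusion.** The gap is real for individual patient-periods. As written, SAP 4.5.9 admits the taper and Follow-up calls of completers who stop GWP42003-P. The size depends on when EOT falls: the only call in Weeks 109–120 for EOT at Day 731, 2 of 3 calls in Weeks 49–60 for EOT at Day 337 (one taper, one off drug), and mere dilution, 2 of 7, for EOT at Day 1457. A period holding only the Follow-up call also escapes LOCF.

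This rests on weekly calls made on schedule and on exactly two calls after EOT. The effect on group frequencies and responder rates cannot be sized, and the divisor effect lies anywhere from none to about 4-fold. The correction is worth making because the affected cells are those of late periods, where a reader looks for maintained effect, and because the SAP already applies the needed cut-off elsewhere.

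**What to change.** In SAP 4.5.9, state that only calls from Day 1 up to the SAP 4.1.4.3 cut-off (the earliest of completion or withdrawal, last call, and last treatment-phase dose) contribute to any 12-week period. State that a period with no such call is missing, including for LOCF. List or summarise the end-of-taper and Follow-up calls separately as post-treatment data, and state their recall period and divisor. Carry the rule to the status epilepticus counts in SAP 4.5.9.1, which use the same periods.

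After this change no post-EOT call remains in the periods. The Day 731 completer has no value in Weeks 109–120 and keeps 9 calls in Weeks 97–108; the Day 1457 completer keeps 5 in Weeks 205–216. The Day 337 completer still has a Weeks 49–60 value from one call describing the week before, so the number of contributing calls should be shown beside sparse periods.

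The cost is a few SAP sentences and one date filter. No new data are needed: SAP 4.1.4.3 and 4.5.8.13 already use the dates. If the SAP can no longer be changed, the filtered tables can be added and the deviation recorded in the study report, as Protocol Section 13 provides.
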